# 4.2.22.4 Primary Analysis of Exploratory Endpoint

Number and proportion of patients who achieve treatment response at Week 52 will be descriptively summarized.

In addition, the number of patients in histological response, patients with tissue eosinophil counts returning to Baseline level or worse (who may be considered as having relapsed) and patients in between these thresholds at Week 24 and Week 52 will be summarized by shift table. Similarly, the number of patients in symptomatic response, patients with symptomatic deterioration and patients in between these thresholds at Week 24 and Week 52 will be summarized by shift table.

The relationship between any changes in symptom scores and change in tissue eosinophils at week 52 will be explored. A scatterplot of changes in SAGED scores and change in tissue eosinophils at week 52 will be evaluated with locally weighted scatter plot smoothing curves (LOESS) for all subjects.

# **4.2.23** Exploratory Endpoint – Use of Concomitant Medications and Dietary Restrictions to Manage EG/EGE

#### **4.2.23.1 Definition**

Background medications for EG/EGE includes systemic and topical ingested or swallowed corticosteroids, PPIs and steroid treatments used for asthma or allergies that are inhaled or administered intranasally.

Dietary restrictions are any changes in diet related to the management of EG/EGE.

#### **4.2.23.2 Derivation**

Information will be directly obtained from collected data.

# 4.2.23.3 Handling of Dropouts and Missing Data

Not Applicable.

## 4.2.23.4 Primary Analysis of Exploratory Endpoint

The number and percentage of patients who reduced the background medications and/or relax dietary restrictions to manage EG/EGE at Week 24 and Week 52 will be summarized descriptively by the randomised treatment received in Part A/B.

# 4.2.24 Exploratory Endpoint – Proportion of Patients with Relevant Healthcare Resource Utilization and Number of Events by HRU Type

#### **4.2.24.1 Definition**

EG/EGE-related and other GI-disease complications-related healthcare resource utilization (HRU) data will be collected in the eCRF by the Investigator and study-site personnel for all participants throughout the study. Protocol-mandated procedures, tests, and encounters are excluded.

The Investigator retrospectively collects any EG/EGE-related and other GI disease complications-related HRU. At baseline, HRU will be collected with a 6-month recall period. At all subsequent visits, any EG/EGE-related and other GI disease complications-related HRU information will be collected with a recall period of 'since last HRU assessment during the scheduled visit'.

The data collected may be used to conduct exploratory economic analyses and will include:

- Number and duration of medical care encounters, including surgeries, and other selected procedures (inpatient and outpatient)
- Duration of hospitalization (total days or length of stay, including duration bywards [e.g., intensive care unit])
- Outpatient medical encounters and interventions (including specialist visits,

General Practitioner visits, home health care visits, and emergency room visits, etc).

• Number and type of diagnostic and therapeutic tests and procedures

HRU will be collected at V2 (Week 0) and every 4 weeks after V2 until V21 (Week 76), then every 12 weeks after V21.

#### **4.2.24.2 Derivation**

Information will be directly obtained from collected data.

# 4.2.24.3 Handling of Dropouts and Missing Data

Not Applicable.

## 4.2.24.4 Primary Analysis of Exploratory Endpoint

Proportion of patients with relevant HRU and number of events by HRU type (including but not limited to hospitalizations, length of hospital stay, office visits, emergency room visits, tests and procedures) will be summarized by randomised treatment and visit.

# 4.2.25 Exploratory Endpoint – WPAI+CIQ Score

#### **4.2.25.1 Definition**

The Work Productivity and Activity Impairment Questionnaire plus Classroom Impairment Questions Version 2 (WPAI+CIQ) consists of questions about how health and health-related issues impact the ability to work, attend classes, and perform regular daily activities. The questionnaire relates to the previous 7 days. The WPAI+CIQ will be used to measure self-reported productivity loss.

This study uses the version of the instrument designed to measure the impact of a specific health problem (SHP). All instances of "problem" in the source text are replaced with "eosinophilic gastritis and/or eosinophilic gastroenteritis" to specify that the participant should respond with EG/EGE symptoms in mind.

There are a maximum of 10 questions and a minimum of 3 questions that will be completed by subjects.

- 1 = currently employed (yes/no)
- 2 = hours missed work due to health problems
- 3 = hours missed work due to other reasons
- 4 = hours actually worked

5 = degree health affected productivity while working (0-10 scale, with 0 meaning no effect)

6 = attends class in an academic setting (yes/no)

7 = hours missed class due to health problems

8 = hours actually attended class

9 = degree health affected productivity while attending class (0-10 scale, with 0 meaning no effect)

10 = degree health affected regular activities (other than work or class) (0-10 scale, with 0 meaning no effect)

If the answer to question 1 is 'No, not currently employed', then the subject should skip to question 6. If the answer to question 6 is 'No, not currently attending class', then the subject should skip to question 10.

The WPAI+CIQ provides 4 types of scores: absenteeism (work or class time missed), presenteeism (impairment at work or class/reduced on-the-job effectiveness), work productivity loss (overall work or class impairment/absenteeism plus presenteeism), and activity impairment. WPAI+CIQ outcomes are expressed as impairment percentages, with higher numbers indicating greater impairment and less productivity.

The WPAI+CIQ score will be collected at V1 (Week -8 to -4), V2 (Week 0) and every 4 weeks after V2 until V21 (Week 76).

#### **4.2.25.2 Derivation**

For the work-related questions, the following calculations should be used to create the outcomes of interest:

- Number of work hours missed = Q2
- Absenteeism = Q2/(Q2+Q4)
- Presenteeism = Q5/10
- Work Productivity Loss = Q2/(Q2+Q4) + [(1-Q2/(Q2+Q4))\*(Q5/10)]

For the class-related questions, the following calculations should be used to create the outcomes of interest:

• Number of class hours missed = Q7

- Absenteeism = Q7/(Q7+Q8)
- Presenteeism = Q9/10
- Class Productivity Loss = Q7/(Q7+Q8) + [(1-Q7/(Q7+Q8))\*(Q9/10)]

Additionally, Activity Impairment = Q10/10.

The composite approach for continuous analyses mentioned in Section 4.2 will be applied.

# 4.2.25.3 Handling of Dropouts and Missing Data

Not Applicable.

# 4.2.25.4 Primary Analysis of Exploratory Endpoint

The WPAI+CIQ score of each type and the change from baseline will be summarized descriptively by visit and randomised treatment group.

# 4.2.26 Exploratory Endpoint – PGI-BR Scores

#### **4.2.26.1 Definition**

The Patient Global Impression of Benefit-Risk (PGI-BR) is a 5-item questionnaire assessing the participant's perception of the overall benefits and risks of treatment. The 5 items assess: overall trial experience, efficacy, side effects, convenience and overall assessment of the benefits and harms of treatment. Items are rated on 5- or 6-point verbal rating or Likert-type scales.

The PGI-BR assessment will be completed by participants Visits 8 (Week 24) and 15 (Week 52) and after discontinuation if applicable as described in Table 4.

#### **4.2.26.2 Derivation**

The PGI-BR items are scored as follows:

Trial experience - "Overall, how would you rate your experience participating in the clinical trial?" (very negative, somewhat negative, neither negative nor positive, somewhat positive, very positive)". Scored from 1 (very negative) to 5 (very positive).

Efficacy – "How much has the study medication helped your condition? (not at all, a little bit, somewhat, quite a bit, very much)". Scored from 1 (not at all) to 5 (very much).

Side Effects – "How bad have the side effects of the study medication been overall? (did not experience any side effects, not at all bad, slightly bad, moderately bad, very bad, extremely bad)". Scored from 5 (did not experience) to 1 (extremely bad).

Convenience – "How convenient or inconvenient has the study medication been? (very inconvenient/somewhat inconvenient/neither convenient nor inconvenient/somewhat convenient)". Scored from 1 (very inconvenient) to 5 (very convenient).

Benefit/risk assessment – "How would you compare the positive and negative things about the study medication? (negatives far greater than positives/negatives somewhat greater than positives/about equal/positives somewhat greater than negatives)". Scored from 1 (negatives far greater than positives) to 5 (positives far greater than negatives).

## 4.2.26.3 Handling of Dropouts and Missing Data

Not Applicable.

## 4.2.26.4 Primary Analysis of Exploratory Endpoint

The PGI-BR score of each category and the change from baseline will be summarized descriptively by visit and randomised treatment group.

# 4.3 Pharmacodynamic Endpoint(s)

Pharmacodynamic exploratory analyses will be described in a separate exploratory analysis plan finalized before database lock.

## 4.4 Pharmacokinetics

Blood samples (processed to serum) for pharmacokinetic assessments will be collected from all subjects at baseline prior to first benralizumab administration at V1 (Week -8 to -4), V4 (Weeks 8), V6(Week 16), V8 (Week 24), V15 (Week 52), V21 (Week 76) and every 12 weeks after. Blood samples will be collected before benralizumab administrations. Results below the lower limit of quantification (BLQ) will be set to LLOQ/2 for analysis and will be listed as <LLOQ.

Serum benralizumab concentration over time will be descriptively summarized for DB period (Part A and Part B) as well as OLE period (Part C). Serum benralizumab concentration will also be summarized by ADA status, see ADA and PK in Section 4.5 for details.

Other pharmacokinetic analyses will be described in a separate exploratory analysis plan finalized before database lock.

# 4.5 Immunogenicity

Anti-drug antibodies to benralizumab will be summarized using descriptive statistics at each visit by study part based on the safety analysis set. The impact of anti-drug antibodies on the pharmacokinetics of benralizumab and eosinophil levels may be

assessed. The potential association of anti-drug antibodies with safety and efficacy may be evaluated.

Serum samples for ADA assessments will be conducted utilizing a tiered approach (screen, confirm, titre) and ADA data will be collected at scheduled visits shown in the CSP. ADA result from each sample will be reported as either positive or negative. If the sample is positive, the ADA titre will be reported as well.

In general, patients with a missing baseline ADA assessment will be assumed to be ADA negative at baseline as a conservative approach to ensure that all subjects are included in all analyses. If a positive ADA titre result is reported as ≤50, then the titre will be imputed as 50 for titre summaries. ADA results from samples collected post-dose instead of pre-dose on an IP administration day are considered unreliable and should be excluded from all derivations.

For each subject, the following ADA responses will be evaluated over the entire on-study period through EOT:

- Subjects who are ADA positive at any time during the study, including baseline and/or post-baseline (also generally referred to as ADA positive). The proportion of ADA-positive subjects in a population is known as ADA prevalence.
- Subjects who are ADA negative at all assessments, including baseline and post-baseline (also generally referred to as ADA negative).
- Subjects who are ADA positive at baseline only.
- Subjects who are ADA positive at baseline and at least one post-baseline assessment.
- Treatment-emergent ADA positive (referred to as ADA incidence). A positive post-baseline result and either of the following statements holds:
  - Baseline is ADA negative and at least one post-baseline assessment is ADA positive. This is called treatment-induced ADA positive.
  - Baseline is ADA positive, and the baseline titre is boosted by greater than
    the variability of the assay (i.e., ≥ 4-fold increase) at ≥1 post-baseline
    timepoint. This is called treatment-boosted ADA positive.
- Subjects who are persistently ADA positive, which is defined as ADA negative at baseline and having at least 2 post-baseline ADA positive measurements with ≥ 16

weeks between first and last positive, or an ADA positive result at the last available post baseline assessment.

- Subjects who are transiently ADA positive, defined as ADA negative at baseline and at least one post- baseline ADA positive measurement and not fulfilling the conditions for persistently positive.
- Subjects who are ADA positive with maximum titre > median of maximum titres. The median of maximum titres will be calculated based on the maximum titre of each ADA positive subject within each treatment group (including both baseline and post-baseline measurements).

The responses above will be summarized as counts and percentages by treatment group. The maximum ADA titre over the on-study period will also be summarized for patients in each of the ADA positive response categories listed above. The maximum titre will be derived based on all available ADA titres reported for each subject, including any unscheduled assessments.

ADA response (positive or negative) and titre will be summarized at baseline and at all scheduled post-baseline visits by treatment group using derived visit windows (refer to Section 3.3.2 for detailed definition of visit windows). In the event a patient has more than one result within a given visit window, the maximum ADA titre will be used in the by-visit summary. In addition, the ADA response will be presented cumulatively. The cumulative ADA response is positive for a specific visit if a positive ADA result is detected at any time point up to and including the specific visit. If all ADA result are negative up to the specific visit, then the cumulative ADA response is negative for that visit. A summary of the number and percentage of patients who are ADA positive at a post-baseline assessment for the first time by visit will also be presented. A line plot of the proportion of subjects who are ADA positive at each visit will be provided.

Key patient information will be listed for patients with positive ADA results, including ADA status, titer, benralizumab serum concentration, and eosinophil level.

All analyses will be conducted on the safety analysis set by treatment group unless otherwise specified. All ADA results will be listed.

# ADA response and demographics/patient characteristics

Demographic and baseline patient characteristics will be presented for the following ADA response categories of patients: treatment-emergent ADA positive, ADA negative, and ADA persistently positive.

# **ADA** and eosinophil levels

Eosinophil levels will be summarised by visit for the following ADA response categories of patients: treatment-emergent ADA positive, ADA negative, ADA persistently positive and ADA positive with titer > median of maximum. A line plot of eosinophil levels by visit and ADA status will also be presented.

# **ADA** and efficacy

The effects of ADA on the primary and key secondary endpoints calculated through EOT will be evaluated through summary statistics by treatment group and ADA status (ADA positive, treatment-emergent ADA positive, ADA negative, ADA persistently positive, and ADA positive with titre > median of maximum titre). Due to the expected small number of ADA positive subjects in the placebo group, no formal statistical comparisons of benralizumab versus placebo by ADA status (positive/negative) are planned.

## ADA and safety

Adverse events and SAEs during the study (separately for on-treatment and on-study periods) will be summarized by ADA status (treatment-emergent ADA positive, ADA negative, ADA persistently positive and ADA positive with titre > median of maximum titre). The on-treatment and on-study periods are as defined in Section 4.2.6.1. AEs and SAEs will also be evaluated by causality as assessed by the investigator. The potential impact of ADA on hypersensitivity will also be assessed.

#### ADA and PK

Benralizumab serum concentrations will be summarised by visit and ADA status (treatment-emergent ADA positive, ADA negative, ADA persistently positive and ADA positive with titre > median of maximum titre) for patients in the PK analysis set.

# 4.6 Safety Analyses

All safety variables will be summarized using the safety analysis set and data presented according to actual treatment received.

The first analysis of safety data will include only data from the double-blind, placebocontrolled first 24 weeks of the study (DB periods from Part A and B, respectively). Patients will be analyzed according to the treatment they actually received (benralizumab or placebo).

Safety data from the open-label benralizumab part of the study (Part C) will primarily be reported separately from Parts A and B. In addition, a key subset of summaries may also be repeated integrating data across the entire study period (i.e. Part A together with Part C

and Part B together with Part C, and also all parts of the study together once part C has completed).

Safety data will be presented using descriptive statistics unless otherwise specified.

All safety measurements will use all available data for analyses, including data from unscheduled visits and repeated measurements.

No safety data will be imputed. The handling of partial/missing dates for AEs and prior/concomitant medications is detailed in Appendix 7.2. Duration of AEs and prior/concomitant medications will not be calculated using imputed dates and will instead be set to missing.

# 4.6.1 Exposure

See Section 4.1.9 for details.

# 4.6.2 Adverse Events

#### 4.6.2.1 Definitions and Derivations

Adverse events experienced by the patients will be collected throughout the entire study and will be coded using the latest version of the Medical Dictionary for Regulatory Activities (MedDRA) per the Data Management Plan.

Adverse event data will be categorized according to their onset date into the following study periods:

- AEs in the pre-treatment period are defined as those with onset day before day of first dose of study treatment.
- AEs in the on-treatment period are defined as those with onset day between day of first dose of study treatment and scheduled end of treatment (EOT) visit for patients who complete study treatment or investigational product discontinuation visit (IPD) for patients who prematurely discontinue study treatment, inclusive. In the event that the EOT or IPD visit is beyond the protocol-defined visit window, AEs with onset after the last dose of study treatment date +28 days +3 days (visit window) will be excluded from the on-treatment period and instead assigned to the post-treatment period.
- AEs in the on-study period are defined as those with onset between day of first dose of study treatment and the day of the scheduled follow-up visit, inclusive.
- AEs in the post-treatment period are defined as those with onset after the ontreatment period defined above.

- On-study AEs in the DB period will be defined as those with onset date between day of first dose of study DB treatment and the day prior to the first dose of OLE period (up to and including day of V9 for patients who do not roll over to OLE).
- On-study AEs in the OLE period are defined as those with onset date on or after the day of the first dose of OLE treatment and up to EOT.

For instances where a patient attends the safety follow-up visit only, but does not attend an earlier IPD visit or EOT visit, adverse events occurring on or after the day of first dose of study treatment and on or before the last dose of study medication + 28 days will be assigned to the on-treatment period, while AEs with onset date after this time will be assigned to the post-treatment period.

If an AE has a missing onset date it will be considered an on-treatment event unless the stop date of the AE indicates otherwise. Similarly, if an AE has a partial onset date it will be considered an on-treatment AE unless the partial onset date or the stop date indicates otherwise.

AEs that have missing causality (after data querying) will be assumed to be related to study drug.

#### 4.6.2.2 Presentation

AEs will be summarized separately for the on-treatment, on-study, and post-treatment periods, as defined in Section 4.6.2.1. Additionally, only serious adverse events (SAEs) in the pre-treatment period (with start date prior to the first dose of IP) will be listed. All AEs will be listed for each subject. Summaries by SOC/PT will be presented by treatment group and will be exposure-adjusted to account for the variability in follow-up periods beyond 24 weeks.

The rate of AEs per person-years at risk will be calculated as (number of patients reporting the AE)/(total IP exposure with patients at risk of AE) for on-treatment and on-study periods. The post-treatment AEs will be listed in listings. The total period at risk for each patient will be the duration of the on-treatment, post-treatment and on-study periods as defined in Section 4.6.2.1. Rates will be expressed in terms of events per 100 patient-years.

An overall summary table will be produced showing the number, percentage, and exposure-adjusted rate of patients with at least 1 AE in any of the following categories: AEs, serious adverse events (SAEs), AEs with outcome of death, and AEs leading to discontinuation of investigational product (DAEs).

AEs, AEs with outcome of death, SAEs and DAEs will be summarised by System Organ Class (SOC) and Preferred Term (PT) assigned to the event by MedDRA. For each PT, the

number, percentage and exposure-adjusted rate of patients reporting at least one occurrence will be presented (ie, multiple occurrences of an AE for a patient will only be counted once). SOC and PT will be sorted by international order.

A summary of the most common AEs will be presented by PT. Additionally, a summary of non-serious AEs occurring in >5% of patients in any treatment group will be presented by PT. AEs and SAEs causing discontinuation of the study treatment and SAEs causing discontinuation from the study will also be summarised by PT.

AEs and SAEs will be summarised by preferred term and investigator's causality assessment (related vs. not related) and maximum intensity. If a patient reports multiple occurrences of the same AE within the same study period, the maximum intensity will be taken as the highest recorded maximum intensity (the order being mild, moderate, and severe).

Other clinically relevant adverse events will include but may not be limited to injection site reactions, hypersensitivity events, serious infections, and malignancies. Adverse events of injection site reactions (high level terms of administration and injection site reactions), hypersensitivity (standardized MedDRA query of hypersensitivity in narrow), serious infections (serious events within the SOC Infections and Infestations), and malignancy (standardized MedDRA query of malignant tumours) will be summarised by preferred term. The summary of injection site reactions will be summarised by injection site location and number of IP administrations. The summary of AEs of hypersensitivity will be presented overall and repeated for events causally related to IP as assessed by the investigator.

Plot of frequencies and risk differences (forest plots) between treatment arms will be presented for the most common adverse events and other specific events of interest. Estimates and confidence intervals based on the Miettinen Nurminen (M-N) method will also be presented for the most common adverse events and any other specific events of interest included in the structured assessment of benefit risk.

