9.4.3.1 Adverse Events

Adverse events will be coded using the most recent version of the Medical Dictionary for Regulatory Activities that will have been released for execution at AstraZeneca/designee.

Adverse events will be presented for each treatment group by system organ class and/or preferred term, including the number and percentage of participants reporting at least 1 event, number of events and exposure-adjusted rates, where appropriate.

An overview of AEs will be presented for each treatment group, including the number and percentage of participants with any AE, AEs with outcome of death, serious AEs, and AEs leading to discontinuation of investigational product.

AE listings for the safety analysis set will cover details for each individual AE, including information on the relationship to investigational product as assessed by the investigator, maximum intensity, seriousness, death and events leading to discontinuation of investigational product, as well as other action taken related to investigational product.

Key participant information will be presented for participants with AEs with outcome of death, serious AEs, and AEs leading to discontinuation of investigational product.

Full details of AE analyses will be provided in the SAP.

Treatment Emergence

The following events are considered treatment emergent:

- AEs with an onset date on or after the first dose of investigational product
- Worsening of pre-existing events on or after first dose of investigational product

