## 4.1.9 Study Drug Compliance

#### 4.1.9.1 Definitions and Derivations

Duration of study drug exposure is calculated in days as:

Study drug exposure = last dose date of IP - first dose date of IP+1.

Treatment compliance is calculated as:

Study treatment compliance = (total doses administered/total doses expected) x 100.

Patients who received no study treatment will have zero compliance. Total number of doses expected includes all visits with protocol scheduled IP administration on or before a patient's IP discontinuation or treatment complete date.

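### The SAP ends open-label on-study AEs at EOT, short of its own OLE period and the follow-up visit, and gives two incompatible denominators for any exposure-adjusted AE rate

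*SAP*

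**What the plan says.** **Windows.** SAP 4.6.2.1 sets the on-treatment window from first dose to the EOT or IP-discontinuation visit, with a cut at last dose plus 31 days if that visit is late. The general on-study window runs from first dose through the follow-up visit. Two further definitions split on-study AEs by study period. The double-blind (DB) one closes the day before the first OLE dose for patients who roll over. The OLE one starts at the first OLE dose and stops at EOT. SAP 4.6.2.2 adds: "AEs will be summarized separately for the on-treatment, on-study, and post-treatment periods". SAP 3.3.1.1 carries OLE to the end of the study, and Protocol 8.3.1 collects AEs through the follow-up period.

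**Rates.** SAP 4.6.2.2 says the rate "will be calculated as (number of patients reporting the AE)/(total IP exposure with patients at risk of AE"). On exposure, SAP 4.6.1 says only "See Section 4.1.9 for details", and SAP 4.1.9.1 gives "Study drug exposure = last dose date of IP - first dose date of IP+1". Later in the same paragraph of 4.6.2.2: "The total period at risk for each patient will be the duration of the on-treatment, post-treatment and on-study periods". The unit is given as events per 100 patient-years, although the numerator counts patients.

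**Whether a rate survives.** The main SAP says: "An overall summary table will be produced showing the number, percentage, and exposure-adjusted rate of patients with at least 1 AE". Protocol 9.4.3.1 allows, for tables by system organ class or preferred term, "number of events and exposure-adjusted rates, where appropriate". For the overview it says "An overview of AEs will be presented for each treatment group, including the number and percentage of participants with any AE" and mentions no rate. The SAP Section 8 addendum carries over main-SAP principles for the retained summaries, naming the safety period definitions, and drops the remaining analyses. Table 11 keeps an any-category AE table for DB and one for OLE, plus an AE listing over both. It states neither the AE window nor whether a rate appears.

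**The concern.** Safety summaries are the main tabulated output of the amended plan, so each AE table needs a defined window. SAP 4.6.2.1 is the only place that defines AEs by DB and OLE period, the labels Table 11 uses. A programmer who follows it for an on-study OLE table would leave out AEs with onset between EOT and follow-up. Two features give that gap some weight. Table 11's SAE key-information table is DB only, so the any-category table is the only OLE table that would count all SAEs. Protocol Table 8 equates 12 weeks with five half-lives, so weeks 4 to 8 after the last dose fall inside that span.

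On rates, dividing by dosing span while counting AEs beyond the last dose would put more time in the numerator than in the denominator. The shortfall is relatively larger for short courses. These can arise by design: under Protocol 6.1.2, patients who move to Part D do not finish their current period. The error would therefore not cancel between arms with different numbers of doses, or between DB and a longer OLE.

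**Working it through.** The plan states no AE rate or person-time figure, so there is nothing to reproduce. The check is a day count from the schedule.

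**Inputs.** Dosing every 4 weeks; exposure formula (SAP 4.1.9.1); EOT 4 weeks after the last dose, window ±3 days, and follow-up 8 weeks after the last dose, window ±7 days (Protocol Table 3). Visits are assumed on time, with no missed doses and no censoring at first event.

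**Formulas for k doses, in days from first dose.**
- Dosing span: 28(k−1)+1
- To the day before the first OLE dose: 28k
- To EOT: 28k+1
- To 8-week follow-up: 28(k−1)+57

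**1. OLE window.** EOT to follow-up is 56−28 = 28 days nominal. At the visit-window limits it is (56−7)−(28+3) = 18 to (56+7)−(28−3) = 38 days.
- Six OLE doses: 28/197 = 14% of the window to follow-up.
- Scheduled maximum of 18 OLE doses (12 at V8-V19, six at V20-V25): 28/533 = 5%.
- If follow-up is at 4 weeks, as Protocol 7.1.2.1 has it after early discontinuation, the nominal gap is 0 days.

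**2. Rate, if shown and if dosing span is the denominator.** DB patient, AEs counted to the day before the first OLE dose:

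| Doses | Dosing span | Window | Ratio |
|---|---|---|---|
| 6 | 141 | 168 | 1.19 |
| 5 | 113 | 140 | 1.24 |
| 4 | 85 | 112 | 1.32 |
| 3 | 57 | 84 | 1.47 |

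Counted to EOT, six doses give 169/141 = 1.20; 18 OLE doses give 505/477 = 1.06. Counted to an 8-week follow-up, six doses give 197/141 = 1.40. Extending the OLE window without correcting the denominator would therefore widen the mismatch.

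Illustration (assumed): three of six patients have an AE and all six receive six doses. On dosing span the rate is 3×36525/(6×141) = 129.5 per 100 patient-years; on the window to EOT it is 3×36525/(6×169) = 108.1.

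**3. Rate, if the period durations are the denominator.** Numerator and denominator cover the same days, the ratio is 1 and there is no inflation. The sentence still leaves a gap. It names three periods that overlap, since on-study contains on-treatment, and does not say which belongs to which rate.

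**The case against.** A reader might infer that the SAP definitely divides AE rates by dosing span and so will report inflated rates. The documents do not support that. The rate paragraph never cites SAP 4.1.9; reaching dosing span takes a separate step through SAP 4.6.1. The same paragraph also defines time at risk by the AE periods, which is the correct idea. What stands is an unresolved contradiction.

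The rate may also be gone. The addendum drops analyses outside its list, Table 11 shows no rate, and the protocol overview gives only number and percentage. Against that, the retained any-category table resembles the main-SAP overview table, which does carry a rate. The question is open.

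A reader might also infer that AEs after EOT are lost. They are not: SAP 4.6.2.2 lists post-treatment AEs, and Table 11 keeps a DB + OLE AE listing. SAP Table 5 gives the safety estimand as on-treatment, which ends at EOT or IP discontinuation, so an on-treatment OLE table would be right to stop there. Table 5 does not settle the matter alone, because SAP 4.6.2.2 also calls for on-study summaries.

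The objection on scale stands in full: 12 patients were randomized, there is no hypothesis testing, and counts and percentages do not depend on the denominator.

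**Conclusion.** The OLE window inconsistency holds. Within SAP 4.6.2.1 the OLE on-study end differs from the general on-study end, and it conflicts with SAP 3.3.1.1; the addendum carries these definitions into the final analysis. Its effect is conditional. A nominal 28 days is left out of the OLE any-category table if that table uses the OLE on-study definition and follow-up is at 8 weeks. Nothing is wrongly dropped if the table is on-treatment.

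The denominator point holds only as a contradiction. The inflation of 19-20% at six DB doses, rising to 47% at three, requires that a rate is reported, that dosing span is used, and that person-time is not censored at first event. Otherwise the figure does not arise or has to be recalculated.

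Severity is minor: the ambiguity affects descriptive summaries, and the listings stay complete.

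**What to change.** - In SAP 4.6.2.1, end the OLE on-study window on the day of the follow-up visit, inclusive, in line with SAP 3.3.1.1.
- In Table 11, state for each AE table whether it is on-treatment or on-study, and whether an exposure-adjusted rate is shown.
- If any rate is shown, replace total IP exposure in SAP 4.6.2.2 with each patient's days at risk in the same window used to count AEs. State whether time is censored at the first event, and label the result patients with event per 100 patient-years.
- Reconcile the follow-up timings, because they fix where the window ends: 4 weeks after last dose in Protocol 7.1.2.1, 8 weeks in Protocol Table 3, and 12 weeks in the Protocol Table 1 footnote for patients not continuing to Part C.

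The cost is SAP wording, one derivation and the protocol reconciliation, with no new data. Any rate shown on dosing span would change, and AEs between EOT and follow-up may be added to the OLE table.
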